### **Central Nervous System Monitoring**

A detailed neurological exam will be conducted and include the following at both protocol-defined time points and whenever deemed necessary by the study investigator:

- Mental status – assessment of orientation, speech, and memory

- Cranial nerves – assessment of cranial nerves II-XII, excluding fundoscopic examination
- Motor system – brief assessment of tone and strength
- Sensory system – brief survey for light touch and temperature of the face, neck, arms, trunk, and legs
- Reflexes – assessment of deep tendon reflexes and plantar responses (Babinski sign)
- Coordination – assessment of upper and lower extremities, including assessment for tremor
- Gait – assessment of tandem gait

## 1.7 Overview and Dose Rationale

TBI-223, as a single agent at 100 mg/kg, demonstrated moderate activity against acute murine TB in BALB/c mice, and in a C3HeB/FeJ mouse model of TB. When combined with the TB drug bedaquiline and the investigational TB drug pretomanid, TBI-223 at 100 mg/kg demonstrated bactericidal and sterilizing activity against murine TB in BALB/c mice that was similar to that of linezolid at the same dose (100 mg/kg). The PK exposure at 100 mg/kg was 179  $\mu\text{g}\cdot\text{hr}/\text{mL}$ , with T>MIC at 61% (or 14.6 hr/day) in the female BALB/c mice.

A dose fractionation study of TBI-223 in a BALB/c mouse model of TB showed that the efficacy drivers were AUC ( $R^2 = 0.92$ ) and T>MIC ( $R^2 = 0.83$ ). The study indicated that a 2 Log lung colony-forming unit (CFU) reduction can be achieved with total a weekly AUC of 868  $\mu\text{g}\cdot\text{hr}/\text{mL}$ , or daily  $\text{AUC}_{0-24\text{hr}}$  of 124  $\mu\text{g}\cdot\text{hr}/\text{mL}$ , with T>MIC of 34% (T>MIC at 8.2 hours over 24 hours).

**Table 3 Exposures**

Cohort	Dose (QD)	C max	AUC (0-24hr)	%T>MIC
Cohort 1	1800 mg (3 x 600 mg SR1)	5.7 µg/mL	63.8 (h*µg/mL)	70%
Cohort 2	2400 mg (3 x 600 mg SR1 and 1 x 600 mg IR)	7.9 µg/mL	93.9 (h*µg/mL)	85%
Cohort 3	3000 mg (4 x 600 mg and 1 x 600 mg IR)	9.7 µg/mL	115.2 (h*µg/mL)	93%

## 2 OBJECTIVE

The primary objective of the study is:

- To evaluate the safety and tolerability of multiple doses of TBI-223 in healthy adult subjects.

The secondary objectives of the study are:

- To determine the pharmacokinetics (PK) of TBI-223 and its metabolite M2 after multiple ascending doses of TBI-223 in healthy adult subjects when administered after a high-calorie, high-fat meal
- For the TBI-223 sustained-release (SR) formulation and for a combination of the SR and immediate-release (IR) formulations, to compare the PK profiles of a single dose when administered to healthy adult subjects in the fasting state versus after a high-calorie, high-fat meal
- To determine the pharmacokinetics (PK) of a single dose of the TBI-223 sustained-release (SR1) formulation in healthy adult subjects when administered fasted.

## 3 STUDY DESIGN SUMMARY

This is a partially-blinded, placebo-controlled, randomized multiple ascending dose (MAD) study to be conducted at one study center.

Thirty-six (36) subjects will be enrolled in 3 cohorts with 12 subjects per cohort. Within each cohort, 9 subjects will be assigned to receive active treatment and 3 subjects will receive placebo. Each subject will participate in one dose level.

The first 2 cohorts (food-effect cohorts) will begin dosing of TBI-223 on Day 1 under fasted conditions, followed by a 3 day washout period and then followed by multiple doses of TBI-223 administered after a high-calorie, high-fat meal from Day 4 through Day 17 (total of 14 days). The third cohort (non-food-effect cohort) will begin dosing of TBI-223 on Day 1 and continue through Day 14, all doses administered after a high-calorie, high-fat meal.

Each subject will be administered TBI-223 or matching placebo with corresponding pharmacokinetic measurements. After each dose cohort, the Sponsor and Investigator will review the pharmacokinetic and safety data before proceeding to the next dose level.

Dose escalation to the next cohort (i.e., dose level) or decisions regarding changed or additional cohorts will not take place until the Sponsor, in conjunction with the Principal Investigator and dose escalating committee, has determined that adequate safety, tolerability, and pharmacokinetics from the previous cohort(s) have been demonstrated to permit proceeding to the next cohort. The Institutional Review Board (IRB) should be immediately notified of the dose escalation or any revised approach for review and approval.

Safety will be assessed throughout the study for all subjects. Safety assessments will include physical and detailed neurological examinations, vital signs (blood pressure, pulse rate, respiration rate, temperature and pulse oximetry), ECGs, cardiac monitoring, adverse events (AEs), and clinical laboratory tests (including hematology, serology, serum chemistry, coagulation, and urinalysis).

Blood and urine will be collected for clinical laboratory evaluations.

The Principal Investigator, in conjunction with the Sponsor may collect additional blood if necessary, for repeat laboratory or safety evaluations including AE follow up.

Female subjects will have blood collected for serum pregnancy testing. Females claiming postmenopausal status will have blood collected to measure follicle stimulating hormone (FSH) levels.

During each cohort, blood samples (trough samples) will be obtained before each dose of study drug, and at the time points on the events schedule ([Table 6](#) for food-effect cohorts and [Table 7](#) for non-food-effect cohort). Plasma pharmacokinetic samples will be analyzed for TBI-223 and M2 using validated analytical methods. Appropriate pharmacokinetic parameters will be calculated using non compartmental methods.

An overview of the dose cohorts is presented in [Table 5](#).

**Table 4 Dose Cohorts**

Cohort a	Dose	
1	Day 1: Single dose of TBI-223, 1800 mg (n=9) (3 x 600 mg SR1 tablets)	Day 1: Single dose of Placebo, 1800 mg (n=3) (3 x placebo tablets for 600 mg IR and SR)
1	Day 4: 14 doses (1 per day) of TBI-223, 1800 mg (n=9) (3 x 600 mg SR1 tablets)	Day 4: 14 doses (1 per day) of Placebo, 1800 mg (n=3) (3 x placebo tablets for 600 mg IR and SR)
2	Day 1: Single dose of TBI-223, 2400 mg (n=9) (3 x 600 mg SR1 tablets and 1 x 600 mg IR tablet)	Day 1: Single dose of Placebo, 2400 mg (n=3) (4 x placebo tablets for 600 mg IR and SR)
2	Day 4: 14 doses (1 per day) of TBI-223, 2400 mg (n=9) (3 x 600 mg SR1 tablets and 1 x 600 mg IR tablet)	Day 4: 14 doses (1 per day) of Placebo, 2400 mg (n=3) (4 x placebo tablets for 600 mg IR and SR)
3	Day 1: Single doses (1 per day) of TBI-223, 3000 mg (n=9) (4 x 600 mg SR1 tablets and 1 x 600 mg IR tablet)	Day 1: 14 doses (1 per day) of Placebo, 3000 mg (n=3) (5 x placebo tablets for 600 mg IR and SR)

a) Additional cohorts may be enrolled if deemed appropriate by the Sponsor to repeat a dose level or to study another dose level.

### 3.1 Dose Escalation

#### Dose Escalation Review

The review of all pertinent safety/tolerability data will include physical examinations, ECGs, vital signs, clinical laboratory tests, cardiac monitoring, and adverse events (AEs or SAEs) through Day 30 (non-food-effect cohort) or Day 33 (food-effect cohorts). Data considered will include data from the current dose cohort and all previous cohorts. The Sponsor and Investigator will determine if there is sufficient data available from all participating subjects to make a dose escalation decision.

Any AEs of grade  $\geq 2$  toxicities (per DMID toxicity table; Appendix 3) must be discussed in the determination of escalation to the next dose level. PK analysis will be completed only on the active treatment subjects and will be blinded by subject. ECG

data will be analyzed in a blinded fashion and unblinded by ECG vendor in order to be presented by treatment group in aggregate (reviewers will not be unblinded by subject).

Upon review of relevant cohort data, the Sponsor, in conjunction with the Investigator, may decide to:

1. Escalate the dose as planned.
2. Evaluate an intermediate dose level prior to proceeding to the next planned dose level based on PK and safety data of preceding groups.
3. Repeat a given dose level in a new cohort of subjects.
4. Increase the dose of the next cohort if the PK is lower than expected in the previous cohort.
5. Add a cohort if the PK is lower than expected after a cohort and there are no safety concerns.
6. Halt the study.

### **3.2 Cohort Stopping Rules for Subjects Receiving Active Drug:**

If any of the cohort stopping rules are met, cohort dosing must be stopped until review of the data by the Sponsor and the Investigator.

Rules for stopping dosing of a cohort include the following:

1. One subject experiences a drug-related SAE.
2. Two or more subjects develop Grade 3 or higher central nervous system AE considered related to drug.
3. Two or more ( $\geq 2$ ) subjects develop QTcF  $> 500$  msec with an increase from baseline  $> 60$  msec after completion of repeat testing.
4. Two or more subjects experience confirmed Grade 3 or Grade 4 cardiac rhythm disturbances considered related to drug.

If any of the cohort stopping rules are met, cohort dosing must be stopped until the data has been reviewed by the Sponsor, Investigator and Dose Escalating meeting (DEM) before dosing is resumed, or other actions taken, or the decision made to discontinue the cohort. Refer to Section [6.2.5](#) for unblinding procedures. The IRB or Ethics committee (EC) should be immediately notified according to their regulations.

## **4 IDENTITY OF INVESTIGATIONAL PRODUCT**

The Investigational Medicinal Product (IMP) will be supplied as TBI-223 tablets or placebo in the following dose strengths and formulations: TBI-223 SR Tablets, 600 mg

(Prototype 1; SR1), TBI-223 IR Tablets, 600 mg (IR), and Placebo Tablets for TBI-223 IR and SR Tablets, 600 mg (Placebo).

Refer to Appendix 2 for details regarding the description and composition of TBI-223.

**Table 5 Identity of Investigational Products**

Test Products:	TBI-223 SR1 Tablet, 600 mg
	Manufactured for Global Alliance for TB Drug Development
	and
	TBI-223 IR Tablet, 600 mg
	Manufactured for Global Alliance for TB Drug Development
Control Product:	Placebo Tablet for TBI-223 IR and SR Tablets, 600 mg
	Manufactured for Global Alliance for TB Drug Development

## 5 SUBJECT SELECTION

### 5.1 Inclusion Criteria

All volunteers must satisfy the following criteria to be considered for study participation:

1. Understands study procedures and voluntarily provides written informed consent prior to the start of any study-specific procedures.
2. Is a healthy adult male or a healthy adult female of non-childbearing potential, 19 to 50 years of age (inclusive) at the time of screening.
3. Has a body mass index (BMI)  $\geq 18.5$  and  $\leq 32.0$  ( $\text{kg}/\text{m}^2$ ) and a body weight of no less than 50.0 kg at the time of screening and check-in.
4. Is medically healthy with no clinically significant screening results, as determined by the Principal Investigator (e.g., laboratory profiles are normal up to and including Grade 1 per DMID toxicity tables; Appendix 3), medical history, vital signs, ECG, or physical/neurological examination findings. Note: If exclusionary lab criteria are met, values may be confirmed by repeat evaluation.
5. Has not used tobacco- or nicotine-containing products (including smoking cessation products), for a minimum of 6 months before dosing.
6. Females of non-childbearing potential, based on having undergone one of the following sterilization procedures at least 6 months before dosing:
  - Hysteroscopic sterilization.
  - Bilateral tubal ligation or bilateral salpingectomy;
  - Hysterectomy; or

- Bilateral oophorectomy.
- Or is postmenopausal with amenorrhea for at least 1 year before the first dose with serum FSH levels consistent with postmenopausal status (i.e., greater than 40 mIU/mL) at screening.

Or, if female of childbearing potential, must agree to use an allowable form of birth control from screening until 14 days after study completion. The following are allowed birth control methods for this study:

- Vasectomized partner (at least 6 months before dosing);
- Non-surgical permanent sterilization (e.g., Essure® procedure) at least 3 months before dosing.
- Double barrier method (e.g., diaphragm with spermicide; condoms with spermicide).
- Intrauterine device (IUD).
- Abstinence (and must agree to use a double barrier method if they become sexually active during the study);
- Implanted or intrauterine hormonal contraceptives in use for at least 6 consecutive months before study dosing; and/or
- Oral, patch, or injected contraceptives, or vaginal hormonal device (i.e. NuvaRing®), in use for at least 3 consecutive months before study dosing.

7. If a non-vasectomized male (or male vasectomized less than 120 days prior to study start) must agree to the following during study participation and for 90 days after the last administration of study drug:

- Use a condom with spermicide while engaging in sexual activity or be sexually abstinent
- Not donate sperm during this time.

*In the event the sexual partner is surgically sterile or postmenopausal, use of a condom with spermicide is not necessary. None of the birth control restrictions listed above are required for vasectomized males whose procedure was performed more than 120 days before study start.*

8. Is willing to answer inclusion and exclusion criteria questionnaire at check-in.
9. Is able to comply with the protocol and the assessments therein, including all restrictions.

10. Is willing and able to remain in the study unit for the entire duration of the assigned confinement period(s), return for outpatient visit(s), and receive a phone call for follow-up questioning about AEs.

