#### Specific Laboratory Abnormalities

23. Serum magnesium, potassium, or calcium laboratory values outside of the normal range at screening. If exclusionary lab criteria are met, values may be confirmed by repeat evaluation.
24. Positive results at screening for human immunodeficiency virus (HIV), hepatitis B surface antigen (HBsAg), or hepatitis C antibodies (HCV).
25. ALT or AST greater than ULN.

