#### 6.7 Blood Sampling, Processing and Shipment

Blood samples will be collected as detailed in [Appendix 1](#).

Refer to the Schedule of Events for specific blood collection time points. The Principal Investigator, in conjunction with the Sponsor, may collect additional blood if necessary for repeat laboratory or safety evaluations including AE follow-up.

After Day -1, blood for clinical labs and coagulation testing should be collected 6-7 hours postdose.

For the food-effect cohorts, a total of 60 mL (15 x 4 mL samples) will be collected from each subject for plasma predose trough pharmacokinetic analysis. A total of 204 mL (51 x 4 mL samples) will be collected from each subject for plasma postdose pharmacokinetic analysis. Approximately 144.2 mL of blood will be collected for the clinical laboratory evaluations. The total volume of blood collected from each subject will not exceed approximately 408.2 mL.

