**Table 6 Total Volume of Blood to be Collected for Testing, Food-Effect Cohorts**

Reason for Collection	Number of Samples	Volume per Sample (mL)	Total Volume (mL)
Clinical labs at screening	1	12.5	12.5
Clinical labs during study (Days -1, 1, 2, 3, 4, 5, 6, 10, 14, 17, 20 and 26/end-of-study)	12	8.5	102
Coagulation (screening and Days -1, 1, 3, 4, 6, 10, 14, 17, 20, and 26)	11	2.7	29.7
Pharmacokinetic analysis (predose, trough)	15	4.0	60.0
Pharmacokinetic analysis (postdose)	51	4.0	204.0
		Total	408.2

For the non-food-effect cohort, a total of 56 mL (14 x 4 mL samples) will be collected from each subject for plasma predose trough pharmacokinetic analysis. A total of 208 mL (52 x 4 mL samples) will be collected from each subject for plasma postdose pharmacokinetic analysis. Approximately 90.9 mL of blood will be collected for the clinical laboratory evaluations. The total volume of blood collected from each subject will not exceed approximately 274.9 mL.

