**Table 11 Definitions for Adverse Event Severity Gradings**

Grade	Severity Rating	Definition
GRADE 1	Mild	Transient or mild discomfort (< 48 hours); no medical intervention/therapy required.
GRADE 2	Moderate	Mild to moderate limitation in activity - some assistance may be needed; no or minimal medical intervention/therapy required.
GRADE 3	Severe	Marked limitation in activity, some assistance usually required; medical intervention/therapy required, hospitalizations possible.
GRADE 4	Potentially Life-Threatening	Extreme limitation in activity, significant assistance required; significant medical intervention/therapy required, hospitalization or hospice care probable.

See Appendix 3 for full DMID Toxicity Tables. The above ratings should be used to estimate the grade for abnormalities NOT found elsewhere in the Toxicity Tables. Lab results within the testing facility's normal range will not be considered AEs when referenced to the DMID assessment/grading scale (Appendix 3).

Laboratory abnormalities and cardiovascular findings of hypertension or hypotension Grade 2 or above on the DMID toxicity tables will be considered AEs.

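### Inclusion 4 accepts DMID Grade 1 blood counts at entry, so a volunteer near the Grade 1 floor can reach a Grade 2 AE from sampling or ordinary count variation alone

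*Protocol*

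**What the plan says.** Protocol section 5.1, criterion 4, requires that the volunteer "Is medically healthy with no clinically significant screening results, as determined by the Principal Investigator", and illustrates this with "laboratory profiles are normal up to and including Grade 1 per DMID toxicity tables".

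The hematology table in Appendix 3 sets the grades in absolute values, without reference to baseline:

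- Hemoglobin: Grade 1 is 9.5-10.5 g/dL, Grade 2 is 8.0-9.4 g/dL.
- ANC: Grade 1 is 1000-1500/mm3, Grade 2 is 750-999/mm3.
- Platelets: Grade 1 is 75,000-99,999/mm3, Grade 2 is 50,000-74,999/mm3.

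The note under Table 11 states: "Laboratory abnormalities and cardiovascular findings of hypertension or hypotension Grade 2 or above on the DMID toxicity tables will be considered AEs". The only exemption there is for values inside the laboratory's normal range. Under section 3.1, AEs of Grade 2 or higher "must be discussed in the determination of escalation to the next dose level".

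For other analytes the protocol overrides the Grade 1 tolerance. Exclusion 23 requires magnesium, potassium and calcium in the normal range, and exclusion 25 bars "ALT or AST greater than ULN". Blood counts have no such line.

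On sampling, section 6.7 says for Cohorts 1-2 "The total volume of blood collected from each subject will not exceed approximately 408.2 mL", and for Cohort 3 "The total volume of blood collected from each subject will not exceed approximately 274.9 mL".

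**The concern.** A toxicity scale is being used as a standard of health. For blood counts, its Grade 1 band describes a volunteer who is already mildly anemic, neutropenic or thrombocytopenic. Because the AE rule uses the same absolute scale, someone at the bottom of Grade 1 is 0.1 g/dL of hemoglobin or 1 neutrophil/mm3 from a Grade 2 AE.

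Safety is the primary objective. Section 1.2 presents TBI-223 as an attempt to avoid the marrow toxicity of its class, and section 1.4 lists myelosuppression among the linezolid label warnings. A Grade 2 anemia or neutropenia that arises without drug effect therefore falls on a signal the development program wants to read cleanly. There is also an avoidable safety cost in taking about 400 mL (Cohorts 1-2) from a volunteer who starts out anemic.

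**Working it through.** **Blood volume, reproduced from the protocol.**
- Cohorts 1-2 (Table 6): 12.5 + 12×8.5 + 11×2.7 + 15×4 + 51×4 = 408.2 mL, as stated.
- Cohort 3 (Table 7): 12.5 + 7×8.5 + 7×2.7 + 14×4 + 32×4 = 274.9 mL, as stated. The section 6.7 text gives 52×4 = 208 mL of postdose PK blood for this cohort, which would total 56 + 208 + 90.9 = 354.9 mL. The Table 13 time points (13 + 20, less one sample shared with a predose draw, = 32) support Table 7, so 274.9 mL is used.

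**Loss between the screening value and the last laboratory value.** Subtract the screening draw (12.5 + 2.7 = 15.2 mL) and the final-visit draw (8.5 + 2.7 = 11.2 mL):
- Cohorts 1-2: 408.2 − 15.2 − 11.2 = 381.8 mL.
- Cohort 3: 274.9 − 15.2 − 11.2 = 248.5 mL.

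**Hemoglobin.** Final value = entry value × exp(−V(1−r)/BV), where V is the loss, r the fraction of red cells replaced and BV the blood volume. Assumed, not in the documents: BV from 3.25 L (50 kg × 65 mL/kg) to 4.9 L (70 kg × 70 mL/kg), and r of 0 or 0.5. The lower weight is the protocol's minimum, "body weight of no less than 50.0 kg at the time of screening and check-in". Results in g/dL, for 3.25 L and then 4.9 L:

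| Cohort, entry value | r = 0 | r = 0.5 |
|---|---|---|
| 1-2, 9.5 | 8.45-8.79 | 8.96-9.14 |
| 1-2, 10.0 | 8.89-9.25 | 9.43-9.62 |
| 1-2, 10.5 | 9.34-9.71 | 9.90-10.10 |
| 3, 9.5 | 8.80-9.03 | 9.14-9.26 |

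Entry at 9.5 ends in Grade 2 in every case. That holds even at 90 kg and 75 mL/kg: 8.98 and 9.24 in Cohorts 1-2, 9.16 and 9.33 in Cohort 3. Entry at 10.0 in Cohorts 1-2 is Grade 2 with no replacement and borderline with half. Entry at 10.5 mostly stays in Grade 1.

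**ANC.** Single draw: p = Φ(ln(1000/m)/σ), with σ = √ln(1 + CV²) and m the usual count. At least one of k draws: 1 − (1−p)^k. Assumed: lognormal within-subject variation, independent draws, no drug effect. For Cohorts 1-2, k = 10 (Table 12, footnote c) or 11 (Table 6 adds Day 5). For Cohort 3, k = 6.

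| CV | m = 1250, k = 10 / 11 | m = 1250, k = 6 | m = 1500, k = 10 / 11 |
|---|---|---|---|
| 10% | 0.12 / 0.13 | 0.07 | <0.001 |
| 15% | 0.50 / 0.54 | 0.34 | 0.03 / 0.04 |
| 20% | 0.75 / 0.78 | 0.57 | 0.19 / 0.20 |
| 25% | 0.87 / 0.89 | 0.70 | 0.40 / 0.43 |

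Example at CV 20%: σ = 0.198, p = Φ(−0.223/0.198) = 0.130, and 1 − 0.870^10 = 0.75.

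**Weight of one such subject.** 1/9 = 11% of a cohort's active arm or 1/3 = 33% of its placebo arm. The subject is on active drug with probability 9/12 = 0.75.

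**The case against.** Entry at Grade 1 is permitted, not assured. Criterion 4 rests on the investigator's judgement, exclusion 1 bars clinically significant hematological disease and conditions that threaten safety or validity, and section 5.3 restricts blood donation beforehand. This stands, but none of these sets a floor for counts, and criterion 4 itself tells the investigator that Grade 1 is acceptable.

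A reader might infer that a Grade 2 count triggers a stop or blocks escalation. It does not: section 3.1 makes it a discussion item, and the stopping rules in section 3.2 contain no hematology criterion.

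A reader might also infer that such an event could not be told apart from a drug effect. The protocol does not support that. Reviewers have screening and Day -1 counts, serial values, data from earlier cohorts, placebo subjects sampled identically, and an unblinded review by two individuals outside the study (section 6.2.5). Section 7.7 has the investigator judge change from baseline and allows repeat tests. What remains is that three placebo subjects per cohort are a weak control, and the Table 11 note makes Grade 2 an AE whatever the baseline.

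The protocol's leading safety concerns are QTc and CNS effects (section 1.6). Section 1.2 ties linezolid's marrow effects to long-term use and reports no significant myelosuppression in 28-day animal studies. Stricter limits for electrolytes fit that priority, so their absence for counts is a design choice, not a contradiction. This lowers the weight of the point.

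Finally, the ANC result depends heavily on the assumed CV and on independence between draws. A volunteer admitted on a single Grade 1 value may also have a higher usual count.

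**Conclusion.** The point holds as an optional improvement. As written, criterion 4 lets a volunteer with low blood counts meet the stated standard of health, one small step from a Grade 2 AE. For hemoglobin at the Grade 1 floor, sampling alone is enough in all three cohorts across the assumed blood volumes and replacement rates. For ANC at the middle of the band, the chance ranges from modest to high depending on an assumed CV.

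The effect should not be extended to every Grade 1 entrant. At 10.5 g/dL it reaches Grade 2 only at the smallest blood volume with no replacement. At ANC 1500 it stays below 5% up to CV 15%, though it rises to about 40% at CV 25%. The figure of about 400 mL belongs to Cohorts 1-2 only. Platelets were not quantified, and the documents do not allow an estimate of how many Grade 1 volunteers would present among 36. The consequence is a harder reading of some AEs and an avoidable burden on anemic volunteers, not an uninterpretable trial.

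**What to change.** Reconcile criterion 4 with the Grade 2 AE and escalation rules by adding one line under Specific Laboratory Abnormalities, parallel to exclusions 23 and 25. It would state that the Grade 1 tolerance does not apply to hemoglobin and platelets at screening, with a confirmatory repeat allowed. The sponsor should set the exact limit. Neutrophils can be included if the sponsor accepts losing volunteers with constitutionally low counts; leaving them out keeps that group eligible but leaves the ANC part of the problem in place. Grade 1 tolerance can remain for the other analytes.

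The cost is one eligibility line in an amendment and a few more screen failures. The tests are already done at screening, so no extra test, visit or subject is needed.
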